8.12. Epworth Sleepiness Scale

The Epworth Sleepiness Scale (ESS) is a self-administered questionnaire composed of 8 questions that provide a measure of a patient’s general level of daytime sleepiness ([Johns 1991](#)).

The ESS is administrated at screening, baseline, weeks 3, 7, 9, 12, 15/ET and 16/EOS.

The ESS is composed of 8 items. The responders are asked to rate their chances of falling asleep while engaged at 8 different activities, on a 4-point scale (0-3). Therefore, the total score can range from 0 to 24.

If at least 1 item has a missing value, then the entire questionnaire is not valid.

Total score of the 8 items and total scores change from baseline will be summarized by time point, using descriptive statistics. In the case of both caregiver and self-administered versions of the ESS are presented at the same visit, caregiver version will be used for patients who are 6 to 12 years old and self-administered version will be used for patients 13 years of age and older.

Total score is calculated as the sum of item scores.

Data will be listed.

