4.2. Specification of Baseline Values

Generally, the baseline value is the last observed data before the first dose of IMP, unless otherwise noted. If the baseline assessments occur on the same day as the first dose of IMP, it is assumed that the patients follow study procedure and those baseline assessments will be used. For patients in the ITT population who took no IMP, the baseline value is the last observed data on or prior to the randomization date. Electrocardiogram/Electrocardiography (ECG) data will follow this rule, unless specified otherwise.

MD-CRS part I and II central reading: for specification of baseline values in case of missing centrally-read MD-CRS part I or II at baseline, see Sections 4.3.1 and 4.3.2.

Baseline values for patients withdrawals and re-enter the study will be defined in Section 4.5.

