6.5.5. The CP module of the PedsQL (QoL, patient/caregiver)

6.5.5.1. Definition

The Pediatric Quality of Life Inventory (PedsQL™) is a health-related quality-of-life instrument that consists of a well-validated generic core measure and some condition and disease-specific modules (Varni et al 2006). The 35-item PedsQL 3.0 CP module encompasses 7 scales: (1) Daily Activities (9 items); (2) School Activities (4 items); (3) Movement and Balance (5 items); (4) Pain and Hurt (4 items); (5) Fatigue (4 items); (6) Eating Activities (5 items); and (7) Speech and Communication (4 items).

The scales comprise parallel child self-report and parent proxy-report formats. Child self-report includes ages 5 to 7 years, 8 to 12 years, and 13 to 18 years. A parent proxy report is included in reports for ages 2 to 4 years (toddler), 5 to 7 years (young child), 8 to 12 years (child), and 13 to 18 years (adolescent, not administered in the study), and assesses parents' perceptions of their child's health-related quality of life (QoL). The instructions ask how much of a problem each item has been during the past 1 month. A 5-point response scale is utilized across child self-report and parent proxy report as follows:

0=never a problem;

1=almost never a problem;

2=sometimes a problem;

3=often a problem;

4=almost always a problem.

To further increase the ease of use for the young child self-report (ages 5–7 years), the response scale is reworded and simplified to a 3-point scale (0=not at all a problem; 2=sometimes a problem; 4=a lot of a problem).

Items are reverse scored and linearly transformed to a 0–100 scale (0=100, 1=75, 2=50, 3=25, 4=0), so that higher scores indicate better quality of life, i.e. fewer symptoms or problems. Scale Scores are computed as the sum of the items divided by the number of items answered (this accounts for missing data). If more than 50% of the items in the scale are missing, the Scale Score is not computed. This computation is consistent with the previous PedsQL peer-reviewed publications as well as other well-established Health-related quality of life measures.

A total score will be computed as the sum of the 35 items divided by the number of items answered and will not be computed if more than 50% of the items are missing. Each teen/child self-report and parent proxy-report will be assessed separately.

The PedsQL is administered at baseline and at week 15/ET visits.

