The incidence of potentially clinically significant abnormal values for ECG variables will be summarized using descriptive statistics with the criteria presented in Table 7. The summary will be completed by treatment and overall, and age groups (6 to < 8 years, 8 to < 12 years, 12 to < 16 years, and ≥ 16 years), and overall using the age at screening.

Table 7: Potentially Clinically Significant Values for ECG Variables by Age

ECG parameter (unit)^a	Age (years old)	Potentially Clinically Significant Low	Potentially Clinically Significant High
HR (bpm)	6 to <8	< 65	> 115
	8 to <12	< 55	> 110
	12 to <16	< 50	> 105
	≥16	< 50	> 100
PR interval (msec)	6 to <8	--	> 160
	8 to <12	--	> 175
	12 to <16	--	> 180
	≥16	--	> 200
QRS interval (msec)	6 to <8	--	> 100
	8 to <12	--	> 105
	12 to <16	--	> 110
	≥16	--	> 120

^a bpm=beats per minute; HR=heart rate; PR interval =Time from the beginning of the P wave to the beginning of the QRS complex in electrocardiogram; RR interval =Time between the start of one R wave and the start of the next R wave in the ECG; QRS duration =Graphical deflections corresponding to ventricular depolarization in a typical electrocardiogram

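### The ESS informant is chosen visit by visit with no same-version rule, so a patient's change from baseline can subtract a self score from a caregiver score or the reverse

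*SAP*

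**What the plan says.** Section 8.12 provides for two versions of the ESS, one completed by the caregiver and one by the patient. The choice between them is governed by a single sentence, which opens: "In the case of both caregiver and self-administered versions of the ESS are presented at the same visit, caregiver version will be used". Its remainder sets an age split, with the caregiver form taken at ages 6 to 12 and the patient's own form from age 13. The sentence does not say whether age is taken at screening, at baseline or at the visit. It also does not say what happens when only one version is present.

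The same section sets the schedule, "The ESS is administrated at screening, baseline, weeks 3, 7, 9, 12, 15/ET and 16/EOS", and the analysis: "Total score of the 8 items and total scores change from baseline will be summarized by time point, using descriptive statistics". It voids incomplete forms: "If at least 1 item has a missing value, then the entire questionnaire is not valid".

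The baseline rule in section 4.2 is general and says nothing about who answered: "the baseline value is the last observed data before the first dose of IMP, unless otherwise noted".

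Elsewhere the SAP settles both issues. For the PedsQL, section 6.5.5.1 states: "Each teen/child self-report and parent proxy-report will be assessed separately". For the ECG age groups, section 8.8 fixes the reference date: "overall using the age at screening". The model age group in section 6.2.3 is defined at baseline.

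**The concern.** A change score is a change in the patient only if the same person rates both times. If the baseline score is the child's own and the week 7 score is the caregiver's, the difference combines any real change in sleepiness with the disagreement between the two raters. The share of such scores can also differ between visits, because form availability can differ between visits.

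Section 1.3 names the ESS as a safety variable, and it is the SAP's dedicated measure of daytime sleepiness. The arms are small (about 43 and 22 patients, section 2.4), so a few mixed scores can be seen in an arm's mean. What is at stake is the readability of a descriptive safety table. No hypothesis test or stopping rule uses the ESS.

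**Working it through.** The plan states no figure on this point, so there is none to reproduce. The check is whether the stated rules can produce a cross-informant change. An illustration of size follows.

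**Step 1: the rules together.** Section 8.12 selects a version within a visit, conditional on both being present. Section 4.2 takes the last pre-dose value, whoever gave it. No sentence links the version used after baseline to the version used at baseline.

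**Step 2: apply the rules to three patients.**

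| Patient | Forms at baseline | Forms at week 7 | Version used after baseline | Change from baseline |
|---|---|---|---|---|
| A, aged 9 | self only | both | caregiver, required by the rule | caregiver minus self |
| B, aged 10 | both, so caregiver is used | self only | self, by default, since no rule is given | self minus caregiver |
| C, turns 13 between the visits | both, so caregiver is used | both | self if age is read at the visit; caregiver if age is fixed at baseline | mixed only on the first reading |

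- Patient A is the decisive case. A matching self form exists at week 7, and the rule sets it aside. This follows from the stated text and does not depend on when age is read.
- Patient B depends on the natural default that a single available form is used. The missing-item rule offers another route to the same result: a caregiver form with one blank item is void, which can leave the self form as the only valid score.
- Patient C depends entirely on the missing reference date.

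**Step 3: how often (illustration; the SAP gives no rate).** Assume that the age-preferred version is absent, and the other used, with probability q at each visit, independently, and that the age category is fixed. A change mixes informants when exactly one of its two visits uses the non-preferred version:

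P(mixed) = q(1 − q) + (1 − q)q = 2q(1 − q)

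| q (assumed) | P(mixed) |
|---|---|
| 5% | 2 × 0.05 × 0.95 = 9.5% |
| 10% | 2 × 0.10 × 0.90 = 18% |
| 20% | 2 × 0.20 × 0.80 = 32% |
| 30% | 2 × 0.30 × 0.70 = 42% |

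If availability is a stable feature of each patient, so that the same form is always the one present, the true figure is lower and could be zero.

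**Step 4: ceiling for the birthday route.** Assume ages spread evenly over the 13 one-year bands from 6 to 18. The share turning 13 in 15 weeks is (15/52) × (1/13) = 2.2%, or 0.022 × 65 = 1.4 patients. This requires age to be read at the visit and both forms to be present at both visits.

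**Step 5: effect of one mixed score.** With an assumed informant gap of g points on the 0 to 24 scale, one mixed score moves the arm mean by g/n. For g = 2 to 4, that is 2/22 = 0.09 to 4/22 = 0.18 points in the placebo arm, and 2/43 = 0.05 to 4/43 = 0.09 points in the active arm. Switches in opposite directions offset each other.

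**The case against.** The best defence is that the sentence in section 8.12 is a tie-breaker for occasional duplicate forms, and that the protocol, which is not shown, may assign one informant per patient. Mixing would then be rare. The SAP also defines age at baseline or at screening elsewhere, and on that reading nobody switches at a birthday. The ESS summary is descriptive, the data are listed, and adverse events are summarised separately in section 8.3.

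Much of this stands. The frequency is unknown, and the consequence is small. The tie-breaker reading does not remove the problem, because in Patient A's case the tie-breaker itself creates the mismatch. The rule also presupposes that both versions will sometimes be present.

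Three stronger readings are tempting, and the document supports none of them:

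- A reader might infer that the version follows the patient's current age, so that about 1.4 of 65 patients switch at their 13th birthday. The age cut is undated, so this is one reading. The figure is a ceiling that also needs both forms at the relevant visits.
- A reader might estimate a shift in an arm's mean of 0.2 to 0.4 points, from 10% mixed scores times a gap of 2 to 4 points. Neither input is in the SAP, and the product holds only if every switch goes the same way.
- A reader might infer a biased comparison between arms. Assignment is randomised and double-blind (section 2.2), and nothing in the SAP suggests that informant switching would differ by arm.

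**Conclusion.** The point holds as a defect in a derivation rule. Sections 8.12 and 4.2 together allow a change from baseline that compares two informants, and in one configuration they require it although a matching form is available. The age cut has no reference date, which adds an avoidable ambiguity.

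The size cannot be determined from the SAP. The 9.5% to 42% range rests on assumed, independent form absence, and the per-patient shift rests on an assumed informant gap. The expected effect is mainly extra noise in a descriptive safety summary. Bias between arms is not shown, and no efficacy, multiplicity or futility conclusion is affected. This is a cheap improvement, not a threat to the trial's conclusions.

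**What to change.** In section 8.12:

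1. Assign one ESS version per patient for the whole study. When both versions exist at baseline, choose by age at baseline: caregiver for 6 to 12 years, self for 13 and older. Otherwise use the only version available at baseline.
2. Compute change from baseline only within the assigned version. Where that version is absent or invalid at a visit, the change at that visit is missing.
3. List scores from the other version, labelled by informant.

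This makes the ESS consistent with the separation of informants already planned for the PedsQL. It needs a few sentences in the SAP and one derivation rule, settled before database lock. Data collection and testing are unchanged. The cost is that a few post-baseline scores from the other version leave the change table.

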8.13. Extrapyramidal Symptom Rating Scale

The Extrapyramidal Symptom Rating Scale (ESRS) consists of 2 subscales, ESRS I and ESRS II.

ESRS I and II are administrated at screening, baseline, weeks 3, 7, 9, 12, 15/ET and 16/EOS.

8.13.1. ESRS I

The first subscale (ESRS I) is a 7 item subjective questionnaire to evaluate parkinsonism, akathisia, dystonia and dyskinesia. The ESRS I is scored on for point scale (0=absent, 1=Mild, 2=Moderate, Severe=3) for each item.

Total score of the 7 items and total scores change from baseline will be summarized by time point, using descriptive statistics.

Total score will be the sum of the 7 items. Missing items will be replaced by the average of the remaining responses within each item.

Data will be listed.

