1.3. Primary and Secondary Study Objectives and Endpoints

The primary and secondary study objectives and endpoints are the following:

Objectives	Measures/Endpoints

The primary objective of the study is to evaluate the efficacy of TEV-50717 to reduce the severity of dyskinetic involuntary movements associated with CP.
	
The primary efficacy endpoint is the change from baseline to week 15 in the MD-CRS part II total score (movement disorder severity, centrally read) (TEV-50717 versus placebo).

A secondary objective is to evaluate the specific efficacy parameters of TEV-50717 beyond the measure of the primary objective.
	
The key secondary efficacy endpoints (TEV-50717 versus placebo) are the following:
 
 • MD-CRS part I total score (general assessment, centrally read) change from baseline to week 15 • CaGI-I (global, caregiver rated) at week 15 • CGI-I (global, physician rated) at week 15 • UHDRS-TMC (centrally read) at week 15 • UHDRS-TMD (centrally read) at week 15 
Other efficacy measures and endpoints (TEV-50717 versus placebo) include the following:
 
 • MD-CRS part I total score (general assessment, physician rated) change from baseline to week 15 • MD-CRS part II total score (general assessment, physician rated) change from baseline to week 15 • MD-CRS Global Index (calculated from MD-CRS parts I and II total scores, centrally read) • MD-CRS Global Index (calculated from MD-CRS parts I and II total scores, physician rated) • UHDRS-TMS (physician rated) • UHDRS-TMC (physician rated) • UHDRS-TMD (physician rated) • PEDI-CAT (ADL, parent/caregiver completed, content-balanced version) • The CP module of the PedsQL (QoL,

Objectives	Measures/Endpoints
	
patient/caregiver)
 
 • PGI-I (global, patient/caregiver) • CGI-S (global, physician rated) • CaGI-I response, defined as patients who are described by the caregiver as “Much Improved” or “Very Much Improved” in the CaGI-I score • CGI-I response, defined as patients who are described as “Much Improved” or “Very Much Improved” in the CGI-I score • CGI-S response, defined as patients who have a reduction of ≥ 1 point in the CGI-S score • PGI-I response, defined as patients who are described as “Much Improved” or “Somewhat Improved” in the PGI-I score

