8.13.2. ESRS II

The second subscale (ESRS II) is a 17-item questionnaire to evaluate parkinsonism and akathisia.

ESRS II consists of the following parts:

1. Tremor: scored on a 7-point item scale for 8 parts of the body. For each part of the body, frequency and amplitude are selected, assigning each one of the 8 items a score from 0=none to 6=severe. Therefore, the total score for tremor can range from 0 to 48.
2. Bradykinesia: scored on a 7-point item scale (0-6).
3. Gait and Posture: scored on a 7-point item scale (0-6).
4. Postural stability: scored on a 7-point item scale (0-6).
5. Rigidity: scored on a 7-point item scale (0-6) for 4 parts of the body. Therefore, the total score for rigidity can range from 0 to 24.
6. Expressive automatic movements: scored on a 7-point item scale (0-6).
7. Akathisia: scored on a 7-point item scale (0-6).

The total score of the 17 items can range from 0 to 102.

Total score of the 17 items and total scores change from baseline will be summarized by time point, using descriptive statistics for continuous variables.

Total score will be the sum of the 17 items. Missing items will be replaced by the average of the remaining responses within each item.

Data will be listed.

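### The only planned ESRS I summary is a total that adds the dystonia and dyskinesia under treatment to parkinsonism and akathisia, so it cannot be read as a safety measure.

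*SAP*

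**What the plan says.** SAP 1.3 lists ESRS among the safety variables. Section 8.13.1 gives the content of the first subscale: "The first subscale (ESRS I) is a 7 item subjective questionnaire to evaluate parkinsonism, akathisia, dystonia and dyskinesia". Each item has four levels, 0 to 3. The score is an unweighted sum ("Total score will be the sum of the 7 items"), and the planned output is that sum and its change: "Total score of the 7 items and total scores change from baseline will be summarized by time point, using descriptive statistics". Beyond that, 8.13.1 says only "Data will be listed". It plans no domain score, item table or count of patients who worsen.

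Section 8.13.2 defines the other subscale more narrowly: "The second subscale (ESRS II) is a 17-item questionnaire to evaluate parkinsonism and akathisia". It too is summarised as a total and its change.

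The primary objective in 1.3 is to "reduce the severity of dyskinetic involuntary movements associated with CP". Section 6.3.1 makes the change in centrally read UHDRS-TMD, a dystonia score, the fifth key secondary endpoint.

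**The concern.** Two of the four domains in the ESRS I total, dyskinesia and dystonia, are what the trial hopes to improve. The other two, parkinsonism and akathisia, are not efficacy targets anywhere in the SAP. On a safety scale they are the signs one would watch for worsening.

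Adding them puts hoped-for benefit and possible harm into one number with opposite signs. If TEV-50717 improves the disease and also causes some parkinsonism or akathisia, the ESRS I total may show no change, or even a change in the drug's favour. If it falls, the table cannot say whether extrapyramidal safety was good or efficacy outweighed harm. What is at stake is the interpretability of one safety table under the safety and tolerability objective. No hypothesis test is involved.

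**Working it through.** **Inputs.** ESRS I: 7 items, each 0 to 3 (8.13.1). ESRS II: 8 tremor items, 4 rigidity items and 5 single items, each 0 to 6 (8.13.2).

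**The SAP's own figure.** ESRS II: 8 + 1 + 1 + 1 + 4 + 1 + 1 = 17 items, and 17 × 6 = 102. This matches the stated maximum. The SAP states no range for ESRS I; it follows as 7 × 3 = 21.

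**Why the total does not identify harm.** Let D be the sum of the dystonia and dyskinesia items and H the sum of the parkinsonism and akathisia items. Then

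change in total = change in D + change in H.

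The same holds for arm means and for the difference between arms. The plan reports only the left-hand side, so any given value fits many combinations of benefit and harm. For example:

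| Patient | Change in D | Change in H | Change in total |
|---|---|---|---|
| Improves on disease, worsens on parkinsonism/akathisia | −2 | +2 | 0 |
| No change on either | 0 | 0 | 0 |

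The planned summary treats these two patients alike.

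**How much could be offset.** The SAP does not say which items belong to which domain. Assume k items are dystonia or dyskinesia and the other 7 − k are parkinsonism or akathisia. The most worsening in H that can be fully offset is min(3k, 3(7 − k)), out of a possible 3(7 − k):

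| k (assumed) | Harm points available, 3(7 − k) | Most that can be offset to 0 |
|---|---|---|
| 1 | 18 | 3 |
| 2 | 15 | 6 |
| 3 | 12 | 9 |
| 4 | 9 | 9 |
| 5 | 6 | 6 |

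These are ceilings. They are reached only if the disease items start high enough to fall that far and the other items start low enough to rise that far. If each of the four domains has at least one item of its own, k lies between 2 and 5. Summarising D and H separately removes the offset at every k.

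**ESRS II side by side.** Its stated content is parkinsonism and akathisia, so it has no D component. The planned output, "Total score of the 17 items and total scores change from baseline will be summarized by time point", is a summary of H-type signs alone, and nothing in it cancels against the treated condition.

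**The case against.** The strongest reply is that the risk is covered elsewhere. ESRS II gives a separate by-visit total for parkinsonism and akathisia. Section 8.3 tabulates adverse events by preferred term, severity and relationship, and parkinsonism or akathisia reported as an adverse event appears there with no offset. ESRS data are listed, and with about 43 and 22 patients (2.4) the listings can be read by hand. The iDMC monitors safety regularly (2.3). ESRS enters no test or decision rule. The size of the offset is also hypothetical: the item split is not given, and the SAP contains no ESRS response data.

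Most of this stands, and it limits the point to ESRS I. A reader might go further and infer that ESRS II masks harm too, because akathisia is one item of 17 and 6 points of 102. The documents do not support that. ESRS II is a sum, so a 3-point akathisia rise moves it by 3 points unless another item falls. A share of the theoretical range says nothing about detectability, which depends on baseline level and spread, and the SAP gives neither.

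The reply does not rescue the ESRS I total itself. Listings and adverse-event tables are not arm-level summaries of this questionnaire, and none of them makes a sum of treated and untreated signs interpretable as safety. Section 8.11 summarises the CBCL by subscale as well as by total, so breaking a scale down is already practice in this plan.

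**Conclusion.** The point holds for 8.13.1. The ESRS I total mixes the signs under treatment with signs that matter as possible harm, so a neutral or falling total cannot be taken as evidence of extrapyramidal safety. The offset can be anything from nothing up to the ceilings above, depending on the undocumented item split and on baseline scores.

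The conclusion rests on two assumptions: that the ESRS I disease items respond when the drug works, and that any drug-induced worsening appears on the other items. The documents provide no data on either.

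This is a modest reporting weakness. It would be wrong to infer that extrapyramidal harm is hidden throughout the plan: ESRS II and the adverse-event tables are free of this cancellation. No test, significance level, estimand or interim rule is affected.

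**What to change.** In 8.13.1, state which of the 7 items belong to which domain. Summarise by visit and arm (a) the parkinsonism and akathisia items and (b) the dystonia and dyskinesia items, as values and changes from baseline. Where an item does not fit one domain, show it on its own. Add the number of patients per arm whose parkinsonism or akathisia items worsen from baseline. Keep the 7-item total as supplementary. Confine the missing-item replacement to items of the same sub-score, so that a missing akathisia item is not filled from dyskinesia responses.

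Optionally, in 8.13.2, also show the akathisia item (0 to 6) apart from the 16 parkinsonism items (16 × 6 = 96, so 0 to 96).

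The cost is the item mapping and a few extra tables from item data already collected. Fixing the split before unblinding avoids a later post-hoc choice.
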